### **Analytical Plans**

All final analyses will be conducted using SAS 9.3; R cmprsk will be used for the competing risk analyses.

- **Baseline Characteristics by Treatment**

The adequacy of randomization is assessed by comparing the distribution of baseline characteristics among the treatment groups: demographics (age, gender, marital status, ethnicity, race, education); physical and medical history measures (weight, BMI, waist/hip ratio, abdominal obesity, systolic and diastolic blood pressure, edema, type of index event (stroke, TIA), presence of carotid angioplasty and carotid endarterectomy before randomization, prior stroke before index event, MI, history of hypertension, history of CHF, atrial fibrillation,

coronary angioplasty, CABG, smoking status, history of coronary artery disease (CABG, angioplasty, or hospitalization for MI) modified MMSE score, NIH stroke scale score, modified Rankin grade; symptoms and complaints (headaches, muscle aches, sinusitis, pharyngitis, teeth problems, shortness of breath); laboratory values (HOMA, glucose, ALT, A1C, hemoglobin); prescription and non-prescription medications (aspirin, multivitamin, anti-hypertensives, loop diuretics, lipid lowering agents, anti-arrhythmic drugs, anti-coagulants, anti-platelets, other). Continuous variables will be examined for skewness, outliers, or other departures from a normal distribution graphically (side-by-side histograms, boxplots, normal quantile plots) and by side-by-side summary statistics (means, standard deviations, medians, quartiles, etc.). Inferences on differences in the means for continuous variables (e.g. age, BMI, weight) by treatment groups are accomplished through two-sample t tests. F tests for equality of variances are used to identify the appropriate statistical tests for continuous measures.

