Because of the size of this study, we expect that the randomization process will produce comparable groups of participants and balance. However, in a secondary sensitivity analysis, we will adjust for the following pre-specified set of baseline variables that may affect prognosis or treatment effect: age, gender, systolic blood pressure, diastolic blood pressure, history of hypertension, type of entry event (i.e., TIA or ischemic stroke), history of prior stroke before the index event, history of coronary artery disease (history of CABG, angioplasty, or hospitalization for MI), and current smoking. In addition, secondary analyses of the effect of treatment in predefined baseline subgroups will be examined by tests of interaction adjusted for multiplicity. The pre-specified subgroups are:

- Age in years
- Gender
- Race (defined as white, black and other)
- Ethnicity (Hispanic vs. non-Hispanic)
- HDL cholesterol
- Fasting plasma glucose
- HOMA
- HbA1c
- Triglyceride
- BMI
- History of hypertension
- History of coronary artery disease (CABG, Angioplasty, or hospitalization for MI)
- Medication adherence (percent of mgs taken based on protocol dosage)
- Medication adherence (<80% vs. ≥80% of mgs taken based on protocol dosage).

Cox proportional hazards models will be used to examine the effect of treatment in these adjusted and subgroup analyses. The Hochberg procedure, a sequentially rejective variation of the Bonferroni procedure, will be used to determine significance using an overall type I error of 0.05 (two-sided). Subgroups analyzed as a continuous measure that are determined to significantly interact with treatment will be further explored based on established clinical cutpoints.

Additional subgroup analyses that will be considered for exploratory tertiary analyses are baseline CRP, baseline statin use, change in HOMA from baseline to year 1, change in CRP from baseline to year 1, change in HbA1c, baseline triglyceride/HDL ratio, baseline non-HDL cholesterol (total cholesterol-HDL cholesterol), atrial fibrillation, and subtype and territory of index event.

- *Analysis of Secondary Outcomes: Stroke, ACS, All-Cause Mortality, Stroke, MI or serious CHF, Diabetes*

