A competing risks sensitivity analysis will be conducted using these two methods. More specifically, Gray's test for subdistribution hazards will be used for comparing the cumulative incidences of each secondary outcome by treatment group and the proportional subdistribution hazards model proposed by Fine & Gray will be used to estimate the treatment effects (subdistribution hazard

ratios). The methodologies described above are available in and will be implemented through the R *cmprsk* package.

Gray's test will be compared with the logrank test for the treatment effect. We will also compare the subdistribution hazard from Fine-Gray model to the cause specific hazard from the Cox model to improve understanding of the treatment effect. A cumulative incidence curve will be compared to Kaplan-Meier curve.

- *Analysis of Secondary Outcomes: Cognitive Decline (Modified MMSE Score)*

To determine whether pioglitazone, compared to placebo, reduces the risk for cognitive decline, as measured by the modified MMSE score, a longitudinal analysis will be done. Repeated measures of the modified mini mental state exam will be analyzed by mixed model methods adjusted for the study design. In addition, secondary analyses will be conducted comparing participants who decline from a normal modified MMSE score ( $\geq 90$ ) to an exit score of  $< 78$  by treatment groups using a logistic model.

The primary analysis will be based on an analysis of covariance mixed model approach using maximum likelihood estimation assuming missing data are missing at random. All participants with available data will be included in the model. Initially, we will determine the most appropriate covariance structure for the repeated outcomes and then fit the mean model. Treatment by time interactions will be examined to determine whether the treatment effect is constant over time. If there is evidence of an interaction ( $p < 0.05$ ), the data will be analyzed by time point.

- *Sensitivity Analysis for Cognitive Data*

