### **Cognitive Decline**

Decline in cognitive functioning will be measured as a change in mean score in the Modified Mini Mental State Examination (3MS). In a secondary analysis, we will restrict the analysis to participants who entered IRIS with a normal 3MS ( $>90$ ) and define a significant decline as an exit score below 78, the customary criterion for significant impairment. The reason to restrict this secondary analysis to participants with a normal baseline score is that any discrete change in score may have different importance for people with different baseline function. A fall of 12 points from normal to less than 78, however, is generally regarded as significant.

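### The cognitive-decline responder model names no covariates; naming baseline 3MS and age would gain a little power at almost no cost

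*SAP*

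**What the plan says.** The SAP's main cognitive analysis is a longitudinal model of the score: "The primary analysis will be based on an analysis of covariance mixed model approach using maximum likelihood estimation". Behind it stands a responder analysis, in the same section (Analysis of Secondary Outcomes: Cognitive Decline): "secondary analyses will be conducted comparing participants who decline from a normal modified MMSE score" to an exit score below 78, "by treatment groups using a logistic model". That sentence neither lists covariates nor says that the model is unadjusted.

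Appendix 1, Cognitive Decline, describes the same analysis. The SAP will "restrict the analysis to participants who entered IRIS with a normal 3MS" and "define a significant decline as an exit score below 78, the customary criterion for significant impairment". It gives a reason for the restriction: "any discrete change in score may have different importance for people with different baseline function".

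Where the SAP plans adjustment for the primary outcome, it lists the variables: "we will adjust for the following pre-specified set of baseline variables that may affect prognosis or treatment effect: age, gender" and others (Analysis of Primary Outcome). Baseline 3MS is not in that list, and nothing carries the list over to the cognitive logistic model. Age and baseline 3MS are both collected. The section on baseline characteristics lists "demographics (age, gender, marital status, ethnicity, race, education" and, among the medical history measures, the modified MMSE score.

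**The concern.** The responder outcome is an absolute exit score, not a change. Within the normal range, a participant who starts near the lower bound needs a much smaller fall to become a responder than one who starts near the top. Baseline 3MS should therefore predict the outcome in this restricted group, and age plausibly does too. If the model holds treatment alone, that information is unused.

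What is at stake is the power of a supporting analysis that may have few events. A second, smaller matter is that an unstated covariate set leaves the choice open until the data have been seen.

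**Working it through.** **No figure to reproduce.** The SAP gives no evaluable number, decline rate, effect size or power for this analysis. Every size below rests on assumptions.

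**Step 1: does baseline still matter inside the normal range?** Assume whole-point scoring and a scale maximum of 100. An exit score below 78 is then 77 or less.
- Start at 90: required fall 90 − 77 = 13 points.
- Start at 100: required fall 100 − 77 = 23 points, and 23/13 = 1.8 times as far.
- If entry requires more than 90, the lowest start is 91: required fall 14 points, and 23/14 = 1.6 times as far.

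So restriction narrows the baseline range but does not make the starting score irrelevant.

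**Step 2: what is adjustment worth?** Logistic models were simulated with and without baseline 3MS and age, 600 replicates per setting. Assumptions:
- 3000 evaluable participants, allocated 1:1
- baseline 3MS uniform on 90-100
- control-arm decline of 2%, 5% or 10%
- conditional treatment odds ratio 0.70 (log odds ratio −0.357)
- log odds ratios of 0.1, 0.2 or 0.3 per 3MS point, paired with 0.3, 0.6 or 0.9 per SD of age

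The SD of a uniform variable on 90-100 is 10/√12 = 2.89 points. The 3MS effects are therefore odds ratios of about 1.3, 1.8 and 2.4 per SD. The two covariates together give c-statistics of about 0.61 to 0.80.

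Efficiency is (mean z adjusted / mean z unadjusted)². It is read as the proportionate increase in sample size that the unadjusted test would need to match the adjusted one.

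| Control decline | Covariates | Log OR (SE) unadjusted | Log OR (SE) adjusted | Efficiency | Power, % |
|---|---|---|---|---|---|
| 2% | weak | −0.379 (0.2911) | −0.380 (0.2917) | 1.001 | 26.2 → 25.7 |
| 2% | moderate | −0.358 (0.2901) | −0.364 (0.2924) | 1.018 | 24.5 → 24.5 |
| 2% | strong | −0.349 (0.2906) | −0.363 (0.2966) | 1.040 | 21.5 → 21.7 |
| 5% | weak | −0.362 (0.1844) | −0.364 (0.1852) | 1.001 | 52.3 → 51.0 |
| 5% | moderate | −0.351 (0.1838) | −0.364 (0.1869) | 1.038 | 48.8 → 49.2 |
| 5% | strong | −0.343 (0.1831) | −0.373 (0.1907) | 1.086 | 47.0 → 49.7 |
| 10% | weak | −0.353 (0.1322) | −0.359 (0.1332) | 1.019 | 76.5 → 77.8 |
| 10% | moderate | −0.334 (0.1313) | −0.357 (0.1353) | 1.073 | 72.3 → 74.7 |
| 10% | strong | −0.314 (0.1311) | −0.358 (0.1401) | 1.137 | 67.2 → 71.7 |

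A single power figure near 50% has a Monte Carlo standard error of √(0.5 × 0.5/600) = 2.0 points, so small differences in the last column should not be over-read.

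A second set, with 3000 participants and an odds ratio of 0.65, gave efficiency gains of about 0-4% at 2% decliners, 1-6% at 4% and 2-12% at 8%. The SE rose by 0.4-6%.

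**Step 3: where does the gain come from?** Take 5% decline with moderate covariates. The estimate grows by 0.364/0.351 = 1.037 and the SE by 0.1869/0.1838 = 1.017. The z ratio is 1.037/1.017 = 1.020, and its square is 1.040, against 1.038 from the mean z values. The SE rises in all nine settings, by 0.2% to 6.9%. The gain is in the test and not in the width of the interval on the log-odds scale.

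**Step 4: is the treatment-only test valid?** With a true odds ratio of 1.0, 5% decline and moderate covariates (1500 replicates), rejection was 5.9% unadjusted and 5.8% adjusted. The Monte Carlo standard error is √(0.05 × 0.95/1500) = 0.6 points, so both agree with 5%.

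**Step 5: how large is chance imbalance?** With 1500 per arm, one standard error of the baseline difference is √(2/1500) = 0.037 SD. For a predictor with odds ratio 2 per SD this shifts the log odds ratio by 0.037 × ln 2 = 0.025. With 4% decliners there are 120 events and the SE is about 2/√120 = 0.18. The shift is about 0.025/0.18 = 14% of one SE.

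**The case against.** The strongest case against is that nothing here is wrong. An unadjusted randomised comparison is valid, and it would match the SAP's approach to the primary outcome, where the principal analysis is unadjusted and adjustment is a sensitivity analysis. The SAP already deals with baseline by restricting to normal scores. Its remark about baseline function justifies that restriction and concerns the clinical importance of a change, not its prognostic strength. The analysis is itself secondary to the mixed model, for one of six secondary outcomes. The gain depends on assumptions and can be nil. All of this stands. It limits the size of the point but does not remove a small gain available from data already collected.

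Three stronger readings are tempting, and the documents do not support them.
- A reader might infer that the SAP excludes baseline 3MS and age. It does not: the sentence is silent. Treatment alone is the natural reading, because covariates are listed where adjustment of the primary outcome is planned, but it is only a reading.
- A reader might infer that precision is lost. For a logistic odds ratio the reverse holds: adjustment slightly raises the SE.
- A reader might infer that the unadjusted result would be biased or its type I error inflated. Step 4 shows no inflation, and Step 5 shows that typical chance imbalance is minor at this sample size.

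**Conclusion.** The point holds as a cheap improvement. The responder model names no covariates, although a fixed exit cut-off leaves baseline 3MS prognostic within the normal range. A treatment-only test is valid and forgoes a little power.

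For 3000 participants, 2-8% decliners and an odds ratio of 0.65, adjustment is worth roughly 0-12% in efficiency, and near zero when decline is rare. In the broader set (odds ratio 0.70, decline up to 10%) the largest gain was 14%, and power changed by between about −1 and +4.5 points. The evaluable number, decline rates, odds ratios, uniform baseline distribution and predictor strengths are all assumptions. The direction is more secure than the size.

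**What to change.** In the SAP's section on cognitive decline, state that the responder logistic model contains treatment, baseline 3MS as a continuous variable, and age, and that the unadjusted odds ratio is reported alongside. Education is also collected, but its contribution was not checked here, so it is not part of this proposal.

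The cost is one line of text, added before treatment codes are opened, and no new data. The small downside is that the adjusted odds ratio is conditional on the covariates and is not the same quantity as the unadjusted one, so the two must be labelled clearly.

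When the sentence is edited, the definition of a normal baseline score should be reconciled too. The analysis section takes 90 or above, while Appendix 1 takes above 90, and this decides whether participants who start at exactly 90 enter the model.

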#### **Secondary Objectives**

1. To determine if pioglitazone, compared to placebo, will reduce the risk for recurrent stroke.

We hypothesize that pioglitazone will reduce the occurrence of recurrent fatal or non-fatal stroke as a discrete outcome.

2. To determine if pioglitazone, compared to placebo, will reduce the risk for acute coronary syndromes (ACS) (acute MI or unstable angina).  
Unstable angina is an important clinical event because it identifies individuals at high risk for MI who need urgent diagnostic and therapeutic intervention. We hypothesize that pioglitazone will reduce the overall occurrence of acute coronary syndromes.
3. To determine if pioglitazone, compared to placebo, will reduce the risk for all-cause mortality.  
We hypothesize that pioglitazone will reduce all-cause mortality because of its vasoprotective effects.
4. To determine if pioglitazone, compared to placebo, will reduce the risk for recurrent stroke, MI, or serious congestive heart failure (CHF).  
We hypothesize that pioglitazone will reduce the occurrence of recurrent fatal or non-fatal stroke, MI or CHF.
5. To determine if pioglitazone, compared to placebo, is effective in preventing progression to overt diabetes.  
Insulin resistance is the principal risk factor for type II diabetes. We hypothesize that pioglitazone, by sensitizing cells to insulin's action, will prevent progression to diabetes.
6. To determine if pioglitazone, compared to placebo, will reduce the risk for cognitive decline.  
We hypothesize that pioglitazone will reduce the risk for cognitive decline by reducing the incidence of clinically apparent and unapparent stroke.

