### Study Outcomes

The primary outcome measure is time to first fatal or non-fatal stroke or fatal or non-fatal MI. There are six secondary outcomes for this study: time to first stroke; time to first episode of Acute Coronary Syndrome (MI or unstable angina); all-cause mortality; the composite of time to first stroke, MI or serious CHF; time to first developing diabetes; and the modified mini mental state exam longitudinal scores. The date of randomization will be used as the time origin for a participant's study period. Time to censoring will be defined as time in days from date of randomization until the date of last contact. Contact will be defined as direct contact with the patient or a pre-defined surrogate. Database review will not be considered sufficient contact to determine event free time except in certain circumstances for all-cause mortality only (see below). Events detected through database searches will be counted if adjudicated as an event.

Participants are to be exited during an exit interview at the end of five years of study participation or at the last scheduled contact that falls between March 9, 2015 and July 7, 2015, whichever comes first.

Maximum follow-up will be 5 years plus a 21 day allowance for late completion of the exit interview (1847 days total).

Outcome and safety events will not be counted in the analysis if they occur after the date of completion of the exit interview. In addition, outcome and safety events will not be counted if they occur more than 21 days after the scheduled date of an exit interview that was not completed or completed late.

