Any stroke, acute coronary syndrome, all-cause mortality, stroke, MI or serious CHF, and progression to diabetes will be analyzed as time to first event in the same manner as the primary endpoint principal analysis. The treatment effect will be summarized as a hazard ratio (pioglitazone vs. placebo) with 95% confidence interval. To provide some control for multiplicity of secondary outcomes, the Hochberg procedure will be used to determine significance using an overall type I error of 0.05 (two-sided).

- Sensitivity Analyses

In addition, depending on the availability of resources, several sensitivity analyses of IRIS outcomes may be conducted using updated criteria that have evolved since initiation of the study (see Appendix 1):

- (1) Analysis of the effect of treatment on risk of the primary outcome (stroke or MI) using adjudicated MI outcomes based on the 2012 ESC/ACCF/AHA/WHF criteria for MI and the 2013 AHA/ASA criteria for stroke.
- (2) Analysis of the effect of treatment on risk of stroke using adjudicated stroke outcomes based on the 2013 AHA/ASA criteria.
- (3) Analysis of the effect of treatment on risk of ACS using adjudicated MI outcomes based on the 2012 ESC/ACCF/AHA/WHF criteria for MI.
- (4) Analysis of the effect on treatment on risk of the composite safety outcome (stroke, MI, serious CHF) with new MI based on the 2012 ESC/ACCF/AHA/WHF criteria and new stroke criteria based on the 2013 AHA/ASA criteria.
- (5) Analysis of the effect of treatment on progression to diabetes using adjudicated diabetes outcomes based on the revised 2010 ADA criteria for diabetes.

- Competing Risks Sensitivity Analysis

The occurrence of individual secondary outcomes (stroke, ACS, stroke, MI or serious CHF, and diabetes) may be circumvented by death. Naively censoring patients who fail from all-cause mortality in analyzing time to first occurrence of any of these secondary outcomes could lead to biased estimates. The Cox model commonly used in classical survival analysis is a valid analysis for cause-specific hazard in the presence of competing risks. But if we are interested in the cause-specific cumulative incidence, the Gray and Fine & Gray methods are more appropriate.

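### The SAP fixes no single treatment test for cognitive decline (3MS): a treatment-by-time pretest can split the analysis into separate visits with no decision rule, and 3MS membership of the Hochberg family is not stated.

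*SAP*

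**What the plan says.** Under Study Outcomes the SAP states that "There are six secondary outcomes for this study", and the longitudinal 3MS scores are the sixth. The rationale in Secondary Objectives is: "We hypothesize that pioglitazone will reduce the risk for cognitive decline by reducing the incidence of clinically apparent and unapparent stroke". Appendix 1, Cognitive Decline, gives the measure: "Decline in cognitive functioning will be measured as a change in mean score in the Modified Mini Mental State Examination (3MS").

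The section on the cognitive outcome in Analytical Plans sets out the analysis:

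- Model: "The primary analysis will be based on an analysis of covariance mixed model approach using maximum likelihood estimation", assuming data missing at random. No coefficient, contrast or visit is named as the test of treatment.
- Covariance: "Initially, we will determine the most appropriate covariance structure for the repeated outcomes and then fit the mean model".
- Pretest: "Treatment by time interactions will be examined to determine whether the treatment effect is constant over time".
- Consequence of an interaction with p below 0.05: "the data will be analyzed by time point". Nothing further is said about that branch.

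Multiplicity is dealt with in the preceding section, whose heading and opening sentence list five time-to-event outcomes and not 3MS: "To provide some control for multiplicity of secondary outcomes, the Hochberg procedure will be used to determine significance", at an overall two-sided 0.05. The cognitive section does not mention Hochberg.

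**The concern.** The five time-to-event outcomes each have one defined test, the log-rank test used for the primary endpoint. The 3MS outcome does not. Its analysis depends on a preliminary test, and one outcome of that test replaces the single model with a set of visit-wise results that the plan does not say how to read.

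The direction of the rule is awkward. If the drug protects cognition by preventing strokes during follow-up, the difference between arms would be expected to widen over time. That is a treatment-by-time interaction, so the hypothesised pattern tends to trigger the branch that has no conclusion rule.

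This also affects the multiplicity plan. If 3MS belongs to the Hochberg family, the visit-wise branch supplies no single p-value to enter. If it does not, a sixth secondary outcome is tested outside the stated control.

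**Working it through.** **Inputs.** The SAP gives no sample size, SD, effect size, visit schedule or correlation for 3MS, so there is no stated figure to reproduce. From the SAP: interaction threshold 0.05; Hochberg at overall 0.05; six secondary outcomes, five of them listed where Hochberg is described; 1:1 allocation; about 4000 participants; follow-up up to 5 years. Assumed for illustration: K = 5 annual post-baseline visits with complete data, 1500 per arm, SD 8, compound symmetry with correlation r = 0.5 to 0.7, and an omnibus 4-df interaction test. Results are given in the order r = 0.5, r = 0.7.

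**Standard errors.**
- One visit: 8 × √(2/1500) = 0.292.
- Average over visits: 0.292 × √((1 + 4r)/5) = 0.226, 0.255.
- Slope per year: 0.292 × √((1 − r)/10) = 0.0653, 0.0506.

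**How often the branch is entered.** For a difference growing by 0.2 points per year, the noncentrality is 0.2² × 10 / (0.292² × (1 − r)) = 9.4, 15.6. On 4 df at 0.05 the pretest is significant in 68%, 90% of trials.

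A wider set of assumptions (3 to 5 visits, r from 0.5 to 0.85, linear growth scaled to 80% power at the last visit) gives 37% to 97% for the omnibus test and 46% to 99.5% for a 1-df linear test. With five visits and r of 0.5 to 0.7, a benefit that starts early and fades triggers the omnibus test in 49% to 74% of trials, as often as a slowed decline of the same size. A constant benefit triggers it in about 5%.

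**Null error of the two-stage rule.** The SAP does not say what counts as success after the pretest, so two readings are shown. Under compound symmetry the average effect and the interaction are independent, so error = 0.95 × 0.05 + 0.05 × P(success given a false interaction).
- Any visit at two-sided 0.05 counts: the conditional probability is about 0.58, 0.38, giving 0.0475 + 0.029 = 7.7% and 0.0475 + 0.019 = 6.7%. Over the wider set of assumptions, including AR(1), the range is 5.6% to 8.4%.
- Only the last visit counts: the conditional probability is about 0.14, 0.10, giving 5.5%, 5.3%.

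**Power of candidate single contrasts, two-sided 0.05.**

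| Contrast | Growing 0.2 per year | Constant 0.8 points |
|---|---|---|
| Average over visits | z = 0.6/0.226 = 2.65; 0.6/0.255 = 2.36: 76%, 65% | z = 3.54, 3.14: 94%, 88% |
| Slope difference | z = 0.2/0.0653 = 3.06; 0.2/0.0506 = 3.95: 86%, 98% | 5% |
| Final visit | z = 1.0/0.292 = 3.42: 93% | z = 0.8/0.292 = 2.74: 78% |

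**Multiplicity.** Smallest Hochberg step: 0.05/5 = 0.0100 with five members, 0.05/6 = 0.0083 with six. If 3MS is tested separately at 0.05 and the two are independent, error over both is at most 1 − 0.95² = 9.75%.

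**The case against.** Several stronger readings are tempting and do not hold.

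- A reader might infer that the analysis splits exactly when the drug slows decline. It does not: the pretest also responds to fading benefit, is positive in 5% of trials with no effect, and can miss real slowing.
- A reader might infer from the headings that 3MS lies outside the Hochberg family. The sentence itself speaks of secondary outcomes in general, and Study Outcomes counts six, so inclusion is also a possible reading. The 9.75% applies only to the separate-test reading, and independence is doubtful because the SAP attributes the cognitive benefit to stroke prevention.
- A reader might take the 7% to 8% error as a property of the plan. It belongs to a rule that any significant visit counts, which the SAP does not state. With Bonferroni across visits the figure is 5.8%, 5.4%.
- A reader might conclude that the plan fails to detect a slowed decline. Under the growing alternative, the two-stage rule finds an effect in 91%, 93% of trials if any visit counts and 89%, 91% if the last visit decides. By-visit estimates are informative too.
- A slope contrast may seem the natural remedy. It has only 5% power against a constant benefit, which in a baseline-adjusted model is also less decline, and the appendix defines the outcome through mean change rather than slope.

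The SAP also has a single logistic comparison of decline from a normal score to an exit score below 78. It is labelled secondary and restricted to participants with a normal baseline score, so it does not supply the missing main test.

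These points limit the finding. They do not supply a decisive contrast, a rule for the visit-wise branch, or a statement of Hochberg membership.

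**Conclusion.** The point stands as a defect in the decision rule. The SAP names no single treatment contrast for 3MS, and a pretest at 0.05 can move the analysis to separate visits without saying which result answers objective 6. Under the assumed 0.2 points per year this happens in roughly 68% to 90% of trials, and the frequency depends heavily on effect size, visit number and correlation. Any inflation of null error is modest and depends on how the branch is read. Membership of 3MS in the Hochberg family is unstated, and on either reading something is missing: a single p-value to enter, or control of the sixth outcome. This concerns one secondary outcome and does not touch the primary endpoint, but it should be settled before unblinding, because a visit or contrast chosen afterwards would be open to challenge as data-driven.

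**What to change.** Revise the cognitive section of Analytical Plans as follows.

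1. Remove the interaction test as a decision rule.
2. Pre-specify one contrast from the baseline-adjusted mixed model that fits a change in mean score and can detect both constant and growing benefit. One example is the adjusted treatment difference at a final visit. Name that visit, since follow-up length varies between participants.
3. Report the treatment-by-time interaction and by-visit differences as descriptive.
4. State that the single 3MS p-value is the sixth member of the Hochberg family, and extend the Hochberg sentence to say so.

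The cost is SAP wording and a smallest Hochberg step of 0.0083 in place of 0.0100. A final-visit contrast also gives up some power against a constant benefit compared with the time-averaged effect (78% versus 94%, 88% under the assumptions above), in return for 93% versus 76%, 65% when the benefit grows. Incomplete data at the final visit would lower its figures. The choice between these two contrasts is open; what matters is that one is fixed in advance.
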